## I. RATIONALE AND BACKGROUND

Navajo families are at increased risk for obesity, diabetes and cancer, in part due to low fruit and vegetable consumption. For children, these behaviors are greatly influenced by their school and home environments. Research has found that as availability and accessibility of fruits and vegetables increases, so does consumption. Furthermore, recent studies of effective child obesity prevention programs, have shown that school-based interventions that incorporate nutrition education and gardening can increase both children and their parents' healthy eating and gardening behaviors. Our study aims to increase consumption of fruits and vegetables, through a curriculum focused on increasing knowledge and self-efficacy to grow and prepare healthy foods, as well as increasing their availability through a school garden.

Poor availability and accessibility of fruits/vegetables is a significant barrier to healthy eating in Navajo communities due their high cost, poor quality, and long distances to reach supermarkets that stock fresh produce. Our previous research suggests that the schools in this area provide an opportunity to increase engagement of both children and their parents in health promotion interventions, including targeting behaviors that, unchecked, lead to obesity early in the lifespan. The impact of this study on knowledge, self-efficacy and behavior around healthy eating will be significant for both the participating school children and their families. Establishing health behaviors, including healthy eating choices, in childhood has been associated with positive health in adulthood and the potential to have a long-term/sustainable impact on health. Children's behaviors can also influence adult family member behaviors. Many intervention studies around diet and physical activity have focused on schoolchildren for this reason.

Incorporating cultural traditions in interventions is vital to sustaining behavioral change. Maintaining language and cultural traditions has been recognized as being important for both a strong ethnic identity and health in racial/ethnic minority populations in the United States. Traditional growing practices, augmented with modern methods of irrigation, and eating traditional foods have been associated with positive health in American Indian populations. Our previous studies have identified a strong interest in promoting Diné language and cultural practices, and school-based gardens have the potential to be effective because they draw on the same cultural traditions and strengths of Navajo communities and intergenerational transfer of knowledge. This model is consistent with other school-based gardens occurring in Native American communities, including the Navajo Nation, and why Navajo adults believe strongly in the importance of educating youth on Navajo farming heritage. The curriculum we have designed and are implementing at a Navajo elementary charter school in Shiprock incorporates elements of Diné philosophy, Navajo language and culture and holds promise in making a significant health impact in the community.

## II. SPECIFIC AIMS

The Navajo Nation (Diné people) has identified gardening and healthy eating as priorities, demonstrated in the recent Diné College Food Sovereignty report, by the junk food and soda tax instituted in 2015, and in the advocacy by tribal leaders for expanding gardens across the Nation. Navajo families are at increased risk for obesity, diabetes and cancer in part due to low fruit and vegetable consumption. Over the past nine years, we have worked with community leaders from the Navajo Nation to research effective ways to promote gardening and healthy eating, and are now poised to estimate the efficacy of a school-based intervention to promote healthy eating and gardening in Navajo children. Previously, we have shown that gardening is a culturally appropriate intervention strategy for improving healthy eating in this population. Community members have shared with us the importance of family in shaping their health behaviors, and a desire to protect the health of the next generation by encouraging healthy eating habits. Therefore, we developed and piloted a school-based intervention to promote gardening and healthy eating among Navajo elementary school children. The "Yéego! Healthy Eating & Gardening" intervention was developed based on social cognitive theory, on previous school-based gardening interventions reported in the literature, and our own formative work in Navajo communities. We collaborated with a Navajo elementary charter school in Shiprock, NM to develop an integrated curriculum and school-based garden incorporating Diné philosophy of thoughtful allocation of local and natural resources. The intervention aims to build students' self-efficacy to grow and eat fruits and vegetables, as well as making other healthy food choices. While Navajo leaders have shown their

commitment to health through adoption of policies to encourage healthy eating among Navajo children, we know that these policies must be paired with successful interventions that are rigorously evaluated to inform additional wellness policy within schools. These interventions and policies, when broadly implemented are expected to reduce the risk of being overweight in children, including Diné children, who are at higher risk for diabetes and for the more than 13 specific cancers linked to obesity. Note: We use Navajo and Diné interchangeably in this grant.

In this study we will estimate changes in healthy eating and gardening behaviors associated with the intervention using a randomized controlled trial design, with the comparison arm receiving a delayed intervention in the following school year. Combining community engagement with rigorous design and analysis is a significant contribution of this study to the Cancer Health Disparities partnership. In parallel with implementing the randomized trial, we will actively maintain the collaborations with our charter Navajo school partners and with our longstanding collaborators in Shiprock, Tsaile and Crownpoint, by inviting them to be advisors and champions for the new trial. In particular, our specific aims are to:

**Aim 1.** Engage and recruit Navajo elementary schools to participate in a randomized controlled trial of “Yéego! Healthy Eating & Gardening” intervention, an integrated healthy eating and gardening curriculum and school-based garden. This phase will include meetings with school leadership, parents and teachers and assessing eligibility. A formal protocol including a run-in period will ensure willingness and capacity to participate in the study for at least two years.

**Aim 2.** Estimate the efficacy of the “Yéego! Healthy Eating & Gardening” intervention to increase healthy eating and gardening behaviors in Navajo elementary school children. The primary outcomes are child measures: a) tendency to choose vegetable and fruit items to eat; b) healthy eating score from a Navajo foods picture sort; c) gardening at home and d) self-efficacy to garden.

We anticipate 4 to 6 schools will participate in the main study. We will also assess process outcomes, including: recruitment, retention and intervention fidelity, and secondary intervention effects on parent healthy eating and gardening behaviors. Assessments will be conducted in a sample of the elementary school children in grades 3 and 4 at each school and in one of their parents (or other adult caregiver in the household that is the index adult for analysis), at the beginning and the end of the first school year. We use a culturally appropriate tool that includes foods commonly eaten by Navajo people to measure food choices in both children and parents. Choosing fruit and vegetables to eat at meal times in children and gardening participation and self-efficacy in children will be assessed using instruments from other studies. Secondary outcomes include measures of child weight and of academic achievement, as well as parent measures of healthy eating and gardening. Analyses estimating the intervention effect will assess the differential change over the first school year between the two groups of schools, adjusting for school level clustering. After the follow-up evaluation, the delayed intervention group will receive the intervention. A final descriptive assessment will be included at the end of the second school year. Continued engagement and skill strengthening will occur through quarterly parent workshops. Attendance at these will be tracked. This proposal is timely as the Navajo Nation consider their policy on dietary and activity benchmarks for schools as part of a rounded curriculum.

### **III. RESEARCH APPROACH**

#### **A. Overview and Design**

The small randomized controlled trial of an intensive curriculum and school garden intervention will be implemented in elementary schools in two communities (Shiprock and Tsaile). The study will begin in year 1 with a period of engagement and recruitment of schools in each community; with the goal of recruiting three schools *in each community* to start the run-in phase (see Figure 1). The run-in period will include time for greater engagement with the school community, an assessment of the potential garden site and an assessment of evaluation readiness. Depending on whether all three schools in the community qualify for the study at the end of run-in, or only two schools per community, we will randomize three or two schools to intervention or delayed intervention status in each community. We will have either two intervention schools and 4 delayed intervention schools, or 2 intervention schools and 2 delayed intervention schools, depending on the run-in information. We will conduct baseline data collection (T1) at the beginning of the school year in Year 2

[figure not shown]
with both children and parents. Students in the intervention group will receive the curriculum and school garden during that academic school year. At the end of the school year, we will conduct the T2 assessment in children and parents. The main evaluation period is between T1 and T2, and the statistical analysis methods refer to the T2 versus T1 change in outcome measures (healthy eating and gardening). After that, at the beginning of the next school year (Year 3), the delayed intervention schools will receive the intervention. During Year 3, we will also conduct quarterly community gardening workshops for adult family members in all schools.

Attendance at these will be tracked. A final assessment (T3) will be conducted at the end of the second school year in all the randomized schools to describe behaviors in children and parents over time, using a quasi-experimental design that estimates change in the delayed intervention group between T2 and T3, attributable in part to the delayed intervention.

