## CONTEXT

New Mexico and Arizona State have mandated closure of all schools for the duration of the school year in response to slowing COVID-19 spread. The study has had to revise its protocol for obtaining the primary outcome measure that includes student follow-up assessment in April/May 2020.

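### The Year 3 estimate is a one-group T2-T3 change that cannot separate the delayed intervention from change shared by all schools, although both arms are measured at T2 and T3

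*Combined protocol and SAP*

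**What the plan says.** Section III.A (Overview and Design) sets out the second school year. The delayed schools start the intervention at its beginning. On workshops it says: "During Year 3, we will also conduct quarterly community gardening workshops for adult family members in all schools". On measurement it says: "A final assessment (T3) will be conducted at the end of the second school year in all the randomized schools". The aim is to describe behaviour over time, "using a quasi-experimental design that estimates change in the delayed intervention group between T2 and T3, attributable in part to the delayed intervention".

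Two other statements limit the role of T3. Specific Aims says: "A final descriptive assessment will be included at the end of the second school year". Section III.A also says that "the statistical analysis methods refer to the T2 versus T1 change in outcome measures". Section IV.E (Analysis Plan) accordingly contains no T2-T3 model, test or interval. Nowhere is the delayed schools' T2-T3 change compared with that of the original intervention schools.

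The COVID-19 Context section states that "New Mexico and Arizona State have mandated closure of all schools for the duration of the school year". The amended Student Follow-up Assessment then moves T2 to online, mail or phone, in place of the individually read interview described in IV.B.

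**The concern.** A one-group change between two dates contains everything that happened between them. Several influences in this interval reach both arms:

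- The Year 3 workshops run in every school, and their replacement is a public video series.
- T2 was taken during closure, by a different survey mode. The Follow-up Assessment Notification section has T2 and T3 follow the baseline procedures, and the COVID-19 change is written for April/May 2020 only. As written, the mode therefore changes again between T2 and T3.
- Every child is a year older (T2 in 2020, T3 in May 2021).

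Some primary outcome items ask about lunch, snack time and gardening at home, where such influences could plausibly act. The attribution wording tells the reader that some of the change belongs to the delayed intervention, but the plan offers no means of saying how much, or whether any does. The Year 3 result could then seem to repeat or contradict the randomised result for reasons unrelated to the curriculum. The concurrent data that would help are already to be collected.

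**Working it through.** The plan states no T2-T3 sample size, effect size, test or intraclass correlation (ICC), so there is no figure to reproduce. The check is algebra, followed by an illustration of precision.

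**What each quantity estimates.** Let *s* be the T2-T3 change common to both arms, *d* the effect of the delayed intervention, and *g* the original intervention schools' own further Year 3 change (continued gain positive, fading negative).

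- Delayed schools' T2-T3 change: *s* + *d*
- Original intervention schools' T2-T3 change: *s* + *g*
- Difference between arms: *d* − *g*

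The one-arm change carries *s* in full. The difference removes *s* but is too small if *g* > 0 and too large if *g* < 0.

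**Inputs from the protocol.**

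- SD 0.48 for the fruit and vegetable choice score, from another study (IV.C).
- Two intervention and four delayed schools, or two and two (III.A). The COVID-19 section refers to six schools, which under III.D means 2 v 4.
- Schools of 40 to 100 pupils in grades 3 and 4 (III.D), with a 60% recruitment goal (IV.B). I use 40 to 80 pupils, so *m* = 24 to 48 children per school (0.6 × 40 and 0.6 × 80).

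**Assumptions not in the documents.** T2-T3 correlation ρ of 0.4 to 0.6, and ICC of change 0 to 0.02.

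**Formulas.**

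- SD of individual change: SDc = 0.48 × √(2(1 − ρ))
- Variance of one school's mean change: V = SDc² × [(1 − ICC)/*m* + ICC]
- SE of the one-arm change with *k* delayed schools: √(V/*k*)
- SE of the difference: √(V/2 + V/*k*)

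The ratio of the two SEs depends only on the number of schools, given equal school sizes:

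- 2 v 4: √[(1/2 + 1/4)/(1/4)] = √3 = 1.73
- 2 v 2: √[(1/2 + 1/2)/(1/2)] = √2 = 1.41

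**Central case** (ρ = 0.5, ICC = 0.01, *m* = 48). SDc = 0.48. V = 0.2304 × (0.99/48 + 0.01) = 0.00706, so √V = 0.084.

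| Schools | SE, one-arm change | SE, difference | 95% half-width of difference |
|---|---|---|---|
| 2 v 4 | 0.084/√4 = 0.042 | 0.084 × √0.75 = 0.073 | 2.776 × 0.0727 = 0.20 (4 df) |
| 2 v 2 | 0.084/√2 = 0.059 | 0.084 | 4.303 × 0.084 = 0.36 (2 df) |

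**Range for 2 v 4.** The extremes are ρ = 0.6, *m* = 48, ICC = 0 and ρ = 0.4, *m* = 24, ICC = 0.02. The one-arm SE runs from 0.031 to 0.065. The SE of the difference runs from 0.054 to 0.112, with half-widths of 0.15 to 0.31 points (2.776 × SE).

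**What a shared shift would do.** Suppose *d* = 0 and *s* = 0.10 points, about 0.2 SD (0.10/0.48 = 0.21). The expected one-arm change is 0.10, all of it unrelated to the intervention. If someone tested it against zero at two-sided 5%, it would be significant in about 34 to 90% of trials over the same range with a normal reference, and about 19 to 59% with 3 between-school degrees of freedom. The plan specifies no such test, so these rates only show that a modest shared shift is large relative to the one-arm SE.

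**The case against.** A reader might infer that the plan counts the whole T2-T3 change as intervention effect. It does not. The wording claims only partial attribution, calls the design quasi-experimental and the assessment descriptive, and keeps the statistical methods to T1-T2. Describing all schools at T3 already implies showing both arms. All of this stands and limits the point to the attribution wording and the missing comparison.

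It is also fair that the original intervention schools are not an untreated control. They had the curriculum in Year 2, and garden help continues over the summer (IV.A, School Gardens), so the difference exchanges *s* for *g*, whose sign is unknown. This rules out making the difference the defined Year 3 effect in place of the one-arm change. It does not remove the value of showing it, because the one-arm change alone cannot remove *s* at all.

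Three further limits stand:

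- A closure-related shift by May 2021 is plausible but not documented. The closure statement covers the 2019-20 school year only, and nothing says whether schools had since reopened.
- Closure fell in the intervention schools' curriculum year, and families chose their T2 mode, so these influences may not be equal across arms. The difference removes only what is common.
- The curriculum is aimed at grades 3 and 4, while T3 notices go to children surveyed at T1. Those in grade 4 at T1 would normally have moved on by Year 3, which blurs exposure in either estimate.

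The precision cost is real. Over the range above with 2 v 4 schools, power for a true difference of 0.10 is only about 11 to 30%. That supports reporting an interval and keeping the descriptive label.

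**Conclusion.** The point holds in a limited form. The Year 3 estimate is a one-group change that takes in shared change in full, so it cannot on its own support even partial attribution to the delayed intervention. This follows from the design and needs no numerical assumption. The size and direction of any shared change are not in the documents; the 0.10 shift, the correlations and the ICCs are assumptions.

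A reader might go further and conclude that the trial's efficacy findings are compromised, or that a false Year 3 claim is likely. The documents support neither. Efficacy rests on the randomised T1-T2 comparison, and no T2-T3 test is planned. The matter is a wording and reporting weakness in a secondary, descriptive objective. It is worth correcting because the data needed are already to be collected.

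**What to change.** In III.A, with a matching sentence in IV.E:

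1. Report T1, T2 and T3 means for both arms side by side.
2. Beside the delayed schools' T2-T3 change, report the difference in T2-T3 change between arms, with an interval that respects clustering by school.
3. State that the difference removes change common to both arms, is understated if the original intervention schools are still improving in Year 3, and is overstated if their gains fade. State that it is imprecise: SE about 1.7 times that of the one-arm change with 2 v 4 schools, 1.4 times with 2 v 2.
4. Present the one-arm change as descriptive, and attribute no part of it to the delayed intervention on that change alone.
5. Record survey mode at T2 and T3, so that a change of mode is visible.

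The cost is protocol and SAP wording, plus one recorded field if mode is not already captured. T3 is already planned in all schools, so no extra assessment is needed. The price is a wide interval, about ±0.15 to ±0.31 points on the 1-4 scale with 2 v 4 schools under the stated assumptions.

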## B. Research Team

The research team includes investigators from NMSU, Fred Hutch and Diné College with complementary expertise in the development and evaluation community and school-based health behavior interventions, gardening, education, and community engagement. The team also includes staff and consultants with

Figure 1: Study Design

expertise in Navajo culture, farming and agriculture. The project will be led by Drs. [name], Associate Professor of Horticulture at NMSU and Director of the NMSU Agricultural Science Center (ASC) sited on the Navajo Nation land and [name], Full Member at the Fred Hutch and Professor of Epidemiology at UW. This study draws on the complementary strengths of all institutions and investigators involved.

### Fred Hutch

[name] role is to provide guidance on study design, dietary assessment and statistical inference, adhering to the most rigorous evaluation methods while honoring the community collaborative nature of this project. Because of her long history of cross-discipline collaboration, she is able to leverage some of the institutional strengths of the Fred Hutch, including cancer prevention randomized trials (group and individual level) and state of the art dietary assessment methodology and statistical expertise. [name], an Associate Member at Fred Hutch and Associate Professor in Health Services at UW brings expertise in community engagement, working with American Indian populations, and designing and implementing health promotion interventions. Her role in the project is to provide guidance in each of these areas.

### New Mexico State University (NMSU)

[name] role is to provide guidance in gardening and horticultural issues, and to continue to foster and grow the already strong relationship with Navajo community partners. The relationships the NMSU ASC has with Navajo tribal leaders are essential for conducting community-engaged research in the region. [name] and his team made up of both NMSU and Diné College scientific staff will be responsible for recruitment of participating elementary schools, assessment at three time points, implementation of the intervention and continued community engagement. All data collection and intervention implementation work will be based at NMSU ASC and Diné College, with assistance provided by FHCRC investigators and staff. [name] will assume responsibility for oversight of the Dine college staff as they contribute to the

activities outlined above.

### Team Meetings

Core investigators and research staff will have weekly team meetings by phone and video conference to make joint decisions about the study. In addition, Fred Hutch investigators and staff will travel semi-annually to the study sites to assist with study coordination.

## **C. Study Sites**

Shiprock is situated at an important road junction (U.S. 499 and U.S. 64). It is home to several important Navajo institutions: the annual Northern Navajo Fair, a branch campus of Diné College, the Bureau of Indian Affairs, an Indian Health Service (IHS) hospital, a branch office of the Tri-State Agricultural Extension Service, a branch office of NMSU Cooperative Extension, and a branch office of the Navajo Special Diabetes Unit. According to 2010 Census estimates, the household population is 8,295 (52% female), with 2,706 housing units. More than 96% of the population is Navajo and about 64% of the population speaks Navajo at home. Also 37% of Shiprock residents live in poverty and about 45% under the age of 65 do not have health insurance, relying on IHS clinics for primary health care. There are significant areas of irrigated farmland due to Shiprock's close proximity to the San Juan River. During the short growing season, common crops are alfalfa for animal grazing, along with corn and squashes. One full-service grocery store sells fruits and vegetables year-round. There are eight fast food restaurants in town. The closest major service center is Farmington, NM about 30 miles from Shiprock.

Tsaile is home to one of the first tribally controlled higher educational institutions, Diné College. Founded in 1968, the institution now operates in seven satellite locations across the Navajo reservation. Tsaile also houses its own land grant extension office as part of the 1994 land grant extension. According to 2010 Census, the household population is 1,198 (55% female), with 335 housing units. More than 72% of the population is Navajo and about 50% of the population speaks Navajo at home. About 46% of Tsaile residents live in poverty, with a median age of 19. Occupations in the administrative, educational, and food service sectors make up the most available job opportunities. Diné College is the largest employer followed by the Tsaile public school and the satellite Indian Health Service clinic. Tsaile is about 25 miles from Chinle and 50 miles from Window Rock grocery stores and restaurants. Food purchases are mainly through gas stations, trading posts and roadside stands. There are no fast food restaurants in Tsaile due to the isolation and remoteness of the community, other economic ventures include livestock production, some farming, and arts and crafts.

